13.4.2. Key Secondary Efficacy Endpoint

- Proportion of days with COWS peak score ≤ 12 during the Treatment Period prior to the VIVITROL injection (Days 1/1a-7)

The analysis will be carried out using a negative binomial model with treatment as a factor.

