7.4. Replacement of Subjects

Randomized subjects who withdraw prior to the completion of the study will not be replaced.

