13. STATISTICS

13.1. Sample Size Considerations

The primary efficacy endpoint of the study is the proportion of subjects who receive and tolerate VIVITROL injection on Day 8/8a as demonstrated by mild (COWS ≤ 12 or SOWS ≤ 10) opioid withdrawal symptoms following VIVITROL administration.

Assuming the proportion of subjects receiving and tolerating VIVITROL administration is 90% in Group 1 and 60% in Group 2, a sample size of approximately 46 subjects per treatment group will provide at least 90% power to detect a statistically significant difference between the two treatment groups at 5% level of significance in a 2-sided test.

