13.2.1. Study Populations

13.2.1.1. Safety Population

The safety population is defined as all randomized subjects who receive at least 1 dose of naltrexone or PBO-N.

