13.4. Efficacy Analyses

Efficacy analyses will be performed using the safety population.

All statistical tests will be 2-sided with a type I error rate of 5%, unless otherwise specified.

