13.4.3. Other Secondary Endpoints

- Proportion of post-VIVITROL days (Days 9-11) in which subjects in each group demonstrate mild (COWS ≤ 12) opioid withdrawal

The analyses will be carried out using a negative binomial model with treatment as a factor.

- Mean peak COWS scores during the Treatment Period and VIVITROL Induction and Post-VIVITROL Observation Period (Days 1/1a-11)
- Area under the curve (AUC) for COWS scores during the Treatment Period and VIVITROL Induction and Post-VIVITROL Observation Period (Days 1/1a-11)
- Mean score for “desire for opioids” VAS during the Treatment Period and VIVITROL Induction and Post-VIVITROL Observation Period (Days 1/1a-11)

These endpoints will be analyzed using an analysis of variance (ANOVA), with treatment as a factor.

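### The negative binomial model named for the proportion-of-days endpoints (7 and 3 days) ignores their upper limit and can lose much of the power when mild days are frequent

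*Protocol*

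**What the plan says.** Section 13.4.2 defines the only designated key secondary endpoint as "Proportion of days with COWS peak score ≤ 12 during the Treatment Period prior to the VIVITROL injection (Days 1/1a-7"). The analysis sentence is "The analysis will be carried out using a negative binomial model with treatment as a factor".

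The first item of Section 13.4.3 is "Proportion of post-VIVITROL days (Days 9-11) in which subjects in each group demonstrate mild (COWS ≤ 12) opioid withdrawal", followed by "The analyses will be carried out using a negative binomial model with treatment as a factor".

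Three other statements bear on how the model would behave:

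- Section 13.4: "Efficacy analyses will be performed using the safety population". Section 13.2.1.1 defines that population as "all randomized subjects who receive at least 1 dose of naltrexone or PBO-N", so early leavers and subjects who never receive VIVITROL stay in.
- Section 7.4: "Randomized subjects who withdraw prior to the completion of the study will not be replaced".
- Section 13.4 sets a two-sided 5% type I error rate for all tests unless otherwise specified.

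Elsewhere the protocol gives proportions a bounded model: logistic regression for the primary endpoint (Section 13.4.1) and for PGART (Section 13.4.4).

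**The concern.** Each subject contributes a number of mild days out of 7, or out of 3. The negative binomial has no ceiling and its variance is never below its mean. When most days are mild, the true variance of such a count is well below its mean. The fitted dispersion then sits at its lower bound of zero, the model becomes Poisson, and its standard error overstates the uncertainty.

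At stake is the key secondary test. It could run far below its stated 5% level and miss a real difference between the arms. The model family is fixed in the protocol text, so this is not a detail left open for the SAP.

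**Working it through.** **Inputs.** From the protocol: 46 subjects per arm (Section 13.1), 1:1 allocation (Section 9.4), two-sided 5% (Section 13.4), windows of m = 7 and m = 3 days. The protocol gives no daily rate of mild days, within-subject correlation (ICC) or dropout rate, and no power figure for these endpoints, so there is no stated figure to reproduce. The rates below are assumed, and ICC is taken as 0.1, 0.3 and 0.5.

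**1. When the variance is below the mean.** For correlated daily indicators with mild rate p, the number of mild days out of m has

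variance/mean = (1 − p)(1 + (m − 1)·ICC).

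This is below 1 once p exceeds p* = 1 − 1/(1 + (m − 1)·ICC).

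| ICC | p*, 7 days | p*, 3 days |
|---|---|---|
| 0.1 | 0.375 | 0.167 |
| 0.3 | 0.643 | 0.375 |
| 0.5 | 0.750 | 0.500 |
| 1 | 0.857 | 0.667 |

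So above 6/7 (7 days) or 2/3 (3 days) no correlation can produce the overdispersion the model is built for.

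**2. Impossible values.** At p = 0.90 the mean is 7 × 0.90 = 6.3. A Poisson with mean 6.3 gives P(Y ≥ 8) = 0.298, so about 30% of the fitted probability lies on 8 or more mild days out of 7.

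**3. Hand calculation of the loss, 90% against 75%, 7 days, complete data.**

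- Log ratio of means: ln(0.90/0.75) = 0.182.
- Standard error used at zero dispersion: √[1/(46 × 6.3) + 1/(46 × 5.25)] = 0.0871.
- True standard error: multiply each term by that arm's variance/mean. At ICC 0.1/0.3/0.5 these ratios are 0.16/0.28/0.40 and 0.40/0.70/1.00, giving 0.0470/0.0622/0.0743.
- Power with the overstated error, Φ[(0.182 − 1.96 × 0.0871)/true SE]: about 60/57/56%.
- Power with the true error, Φ[0.182/true SE − 1.96]: about 97/83/69%.

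With both arms at 90%, the standard error is too large by 1/√0.16, 1/√0.28 and 1/√0.40, that is 2.5, 1.9 and 1.6 times. The nominal 5% test then rejects in about 0.0/0.0/0.2% of trials.

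**4. Simulation.** Days were beta-binomial, 46 per arm, 1,500 or 2,000 trials per scenario. The negative binomial (NB) was fitted by maximum likelihood with dispersion at or above zero and a Wald test. The comparator was quasi-binomial logistic regression (QB) with Pearson dispersion and a t-test. Leavers were observed for 1 to 6 days, drawn uniformly. Results are at ICC 0.1/0.3/0.5.

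| Scenario (mild days counted unless stated) | NB power % | QB power % |
|---|---|---|
| 7 days, complete, 90 vs 75% | 61/57/54 | 97/85/69 |
| 85 vs 65% | 94/89/81 | 99.7/95/82 |
| 80 vs 60% | 94/88/78 | 99/91/80 |
| 70 vs 50% | 96/86/66 | 99/85/72 |
| 90 vs 75%, dropout 10%/10%, missing days not mild | 55/52/52 | 86/68/57 |
| same, dropout 20%/20% | 49/52/45 | 68/58/46 |
| same, dropout 10%/30% | 96/93/88 | 99/96/89 |
| 90 vs 75%, dropout 10%/30%, observed days only (offset) | 50/51/53 | 96/84/71 |
| 90 vs 75%, complete, days above 12 counted | 98/81/63 | 98/83/71 |
| Days 9-11, receipt 90 vs 60%, non-recipients 0 of 3, 95% mild among recipients | 83/83/84 | 90/89/89 |
| Days 9-11, recipients only (46 × 0.9 ≈ 41 vs 46 × 0.6 ≈ 28), 90 vs 70% | 23/26/25 | 92/80/69 |

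The 90% and 60% receipt rates are borrowed from the primary endpoint assumption in Section 13.1.

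NB type I error, 7 days, complete data: 0.0/0.1/0.2% with both arms at 90%, 0.1/0.8/3.4% at 80%, 2.6/4.7/2.8% at 50%. No scenario exceeded 5.4%. In the complete 90% against 75% case the dispersion estimate was zero in 98-100% of trials.

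**5. Independent check with other comparators.** For 90% against 80% over 7 days, NB power was 11/18/23%. A subject-clustered difference in proportions gave 80/56/44% and a Wilcoxon test on each subject's proportion 81/61/51%. With both arms at 90%, NB rejected in 0.0-0.4% of trials and the two comparators in about 5%.

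**The case against.** The strongest reply is that the loss comes from the model-based standard error, which the protocol does not specify. Keeping the negative binomial means and using a robust variance gives, for 90% against 75% with complete data, power of 98/85/70% and, with both arms at 90%, type I error of 4.9/4.3/4.4%, as good as the quasi-binomial. This is true, and it shows a second possible repair. But the protocol states no robust variance, and the named model would still ignore the ceiling of 7 or 3 days.

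Second, the large loss needs frequent mild days, and the 7-day endpoint uses the daily peak of many readings (Sections 8.2.2 and 8.4), so one reading above 12 makes a day not mild. The Day 1 entry requirement of COWS at or below 12 is a single score before any study drug and does not establish a 90% rate. This stands as a limit on the size. At 85% against 65% and lower, the gap is at most about 6 points.

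Third, the protocol does not fix whether mild days or days above 12 are counted, or how unobserved days enter, and a SAP may settle both. Counting days above 12 removes most of the loss at ICC 0.1-0.3. For Days 9-11, scoring non-recipients as 0 of 3 leaves a loss of 5-7 points in the scenario with the borrowed receipt rates; the very large figure applies only if the analysis is in effect limited to recipients, which Section 13.4 does not say.

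These points bear on magnitude. None makes the negative binomial a suitable family for a proportion of a fixed number of days.

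**Conclusion.** The concern holds. The protocol assigns an unbounded count model to two proportions with fixed denominators, one of them the only key secondary endpoint.

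The mismatch is certain from the text; the size of its effect is conditional. For the 7-day endpoint with 90% against 75% mild days and complete data, the power loss is about 36, 28 and 15 points at ICC 0.1, 0.3 and 0.5, and the test runs at close to 0% when both arms are at 90%. A similar or larger loss remains if leavers are analysed on observed days only. The loss is much smaller nearer 50-70% mild days, or when many leavers' missing days are scored as not mild.

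All of this rests on assumed daily rates, ICC and dropout, beta-binomial days, and a model-based Wald test. The error is towards conservatism: false positives do not rise, and the primary endpoint and the sample size are not touched. It should be fixed, but it does not threaten the main result.

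**What to change.** In Section 13.4.2 and under the first item of Section 13.4.3, replace the negative binomial model with a quasi-binomial or beta-binomial logistic model of mild days out of the days in the period, with treatment as a factor. A GEE logistic model of the daily yes/no indicator would also serve.

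The cost is a wording change in two places, made before unblinding. It needs no new data and no extra subjects. In the scenarios run, the quasi-binomial was never materially worse than the negative binomial, and in repeat simulations it held its type I error near 5%.

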13.4.3. Other Secondary Endpoints

- Proportion of post-VIVITROL days (Days 9-11) in which subjects in each group demonstrate mild (COWS ≤ 12) opioid withdrawal

The analyses will be carried out using a negative binomial model with treatment as a factor.

- Mean peak COWS scores during the Treatment Period and VIVITROL Induction and Post-VIVITROL Observation Period (Days 1/1a-11)
- Area under the curve (AUC) for COWS scores during the Treatment Period and VIVITROL Induction and Post-VIVITROL Observation Period (Days 1/1a-11)
- Mean score for “desire for opioids” VAS during the Treatment Period and VIVITROL Induction and Post-VIVITROL Observation Period (Days 1/1a-11)

These endpoints will be analyzed using an analysis of variance (ANOVA), with treatment as a factor.

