8.3. Day 8/8a Naloxone Challenge and VIVITROL Injection

8.3.1. Naloxone Challenge

Prior to the start of the naloxone challenge, COWS/SOWS assessments will be administered. Subjects who are no longer exhibiting significant signs of withdrawal as demonstrated by COWS total score ≤ 12 on Day 8/8a will undergo a 2-part naloxone challenge as follows:

Part 1:

- Administer 1.5 mg* of naloxone intramuscularly in the subject's arm (nondominant arm preferred for first injection)
 - * Note: Each naloxone injection consists of 1.5 mg. Doses of naloxone sufficient to precipitate opioid withdrawal in the presence of short-acting opioids may not suffice to displace BUP from the μ -opioid receptor (Gal 1989).
- Administer COWS and SOWS at 10 and 20 minutes post-naloxone injection. Vital signs will be measured and the subject will remain under observation following the naloxone injection to monitor for safety
 - At each timepoint (10 and 20 minutes) the COWS score must be no more than 2 points greater than the pre-naloxone baseline COWS score for subjects to qualify for Part 2.
 - If either the 10- or 20-minute COWS score increases by >2 points from the pre-naloxone COWS, then the challenge is considered to be positive (see [Section 8.3.3.1](#) for instructions on how to proceed following a positive naloxone challenge). A positive challenge is indicative of a significant increase in withdrawal symptoms and physical dependence on opioids.

Part 2:

- Administer second naloxone injection (1.5 mg [see Part 1 above regarding dose] naloxone in opposite arm to that used for first injection)
- Administer COWS and SOWS at 10 and 20 minutes post-naloxone injection. Vital signs will be measured and the subject will remain under observation following the naloxone injection to monitor for safety
 - At each timepoint (10 and 20 minutes) the COWS score must be no more than 2 points greater than the immediately previous Part 1 COWS score for subjects to qualify for VIVITROL injection
 - If either the 10- or 20-minute COWS score in Part 2 increases by >2 points from the immediately previous Part 1 COWS score, then the challenge is considered to be positive. See [Section 8.3.3.1](#) for how to proceed following a positive naloxone challenge.

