Eligibility for VIVITROL administration on Day 8/8a will consist of the following: Part 1 post-naloxone COWS scores increase by ≤ 2 points from pre-naloxone scores and Part 2 post-naloxone COWS scores increase by ≤ 2 points from the immediately previous Part 1 score, with a total allowable increase of

≤4 points in COWS total score for Parts 1 and 2 of the challenge combined. Subjects must have a total COWS score ≤16 following the naloxone challenge to qualify for VIVITROL administration. Subjects with a positive naloxone challenge on Day 8 will have the opportunity to retry the challenge on the following day (Day 8a; see [Section 8.3.3.1](#))

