8.3.2. VIVITROL Injection

If the naloxone challenge is negative, a single intramuscular (gluteal) injection of VIVITROL 380 mg will be administered following the naloxone challenge on Day 8/8a. Subjects will remain on-site for 1 hour for safety observation following VIVITROL administration and then may be discharged home, following PM withdrawal assessments. They will be asked to return for outpatient visits on the 3 days following VIVITROL injection (Days 9-11).

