8.3.3. Subjects Who Do Not Transition to VIVITROL

Due to loss of opioid tolerance and a heightened risk for overdose in subjects who have transitioned from BUP but have not received VIVITROL (due to subject withdrawal of consent or a positive naloxone challenge), it is important that subjects be reinstated on BUP/Nx maintenance therapy and discharged to their treatment provider to continue BUP maintenance and discuss future treatment options.

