8.3.3.1. Treatment Options for Subjects with a Positive Naloxone Challenge

8.3.3.1.1. Day 8

Subjects with a positive naloxone challenge on Day 8 will not receive the VIVITROL injection that day. In such cases, these subjects will receive Day 7 study drug (naltrexone/PBO-N), and complete Day 7 assessments and procedures (per [Figure 2](#)). Pre- and postdose COWS will be assessed for clinical safety purposes only. Day 8 assessments and procedures will be repeated the following day (Day 8a).

For subjects who do not wish to receive a naloxone challenge on Day 8a, the study staff will notify the subject's BUP provider prior to discharge, to inform him/her of the treatment and medications the subject has received during the course of the study, and of the need for a follow-up appointment. Such subjects will be restarted on BUP/Nx while on the residential unit at a dose deemed clinically sufficient. Depending upon how many days of blinded treatment medication they have received, the investigator may decide that, for safety reasons, the subject should remain in the residential unit for up to 48 hours. Upon discharge he/she will be provided up to 3 days of BUP maintenance. The subject may choose to discuss other future treatment options with his/her BUP provider.

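### The Days 9-11 post-VIVITROL endpoint is tested in all dosed subjects, but only injected subjects have such days, and injection is decided after randomization on COWS

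*Protocol*

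**What the plan says.** Protocol Section 13.4.3 lists among the other secondary endpoints "Proportion of post-VIVITROL days (Days 9-11) in which subjects in each group demonstrate mild (COWS ≤ 12) opioid withdrawal", to be analysed with a negative binomial model that has treatment as its factor. Section 13.4 fixes the analysis set: "Efficacy analyses will be performed using the safety population". Section 13.2.1.1 defines it: "The safety population is defined as all randomized subjects who receive at least 1 dose of naltrexone or PBO-N". Receipt of the injection is not part of that definition.

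Who is injected is settled on Day 8/8a. Under Section 8.3.1, only subjects without significant withdrawal, as "demonstrated by COWS total score ≤ 12 on Day 8/8a will undergo a 2-part naloxone challenge". COWS may then rise by no more than 2 points in each part, and "Subjects must have a total COWS score ≤16 following the naloxone challenge to qualify for VIVITROL administration".

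Of injected subjects, Section 8.3.2 says: "They will be asked to return for outpatient visits on the 3 days following VIVITROL injection (Days 9-11". Of the others, Section 8.3.3 says that "it is important that subjects be reinstated on BUP/Nx maintenance therapy and discharged to their treatment provider", and Section 8.3.3.1 adds that "the investigator may decide that, for safety reasons, the subject should remain in the residential unit for up to 48 hours". Table 4 marks COWS for Days 9/ET, 10 and 11 without limiting those columns to injected subjects.

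**The concern.** The endpoint and the analysis set do not fit together. For a subject who was not injected, the number of post-VIVITROL days is zero, so the proportion is 0 divided by 0. If the number of days is the exposure in the negative binomial model, such a subject contributes nothing to the fit. The comparison then rests on those who were injected.

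Those subjects are selected after randomization and after treatment, on the scale that the endpoint uses. The entry limit for the challenge is the same COWS cutoff of 12. The protocol also expects the two arms to differ in how many subjects get through. If naltrexone brings more subjects to injection, a comparison among recipients gives no credit for it. If the additional recipients are the more symptomatic ones, naltrexone can even look worse.

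The primary endpoint does not have this problem, because it requires both receipt and tolerance. A subject without an injection is a defined failure there. The Days 9-11 endpoint has no such wording.

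**Working it through.** **1. The plan's own figure.** Section 13.1 assumes 90% vs 60% of subjects receiving and tolerating the injection, 46 per group, two-sided 5%, at least 90% power. With pooled p = 0.75:
- SE under the null = √(2·0.75·0.25/46) = 0.0903
- SE under the alternative = √((0.90·0.10 + 0.60·0.40)/46) = 0.0847
- z = (0.30 − 1.96·0.0903)/0.0847 = 1.45, so power is 92.7%

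Fisher's exact test gives 89.8%. The stated figure is consistent. The protocol gives no figure for the Days 9-11 endpoint.

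**2. Subjects without a post-VIVITROL day, at the planned rates.**
- All failures uninjected: 46·0.10 = 4.6 vs 46·0.40 = 18.4, together 23 of 92 (25%). This is an upper limit, because the planned rates combine receipt with tolerance.
- Half of the failures uninjected: 46·0.05 = 2.3 vs 46·0.20 = 9.2.

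**3. Effect of the handling rule.** The mild-day rates here are assumptions; the protocol gives none. Take 90% mild days in placebo recipients and in the matching share of the naltrexone arm, and x in naltrexone's additional recipients.
- All failures uninjected. Recipients only: (0.60·0.90 + 0.30·x)/0.90 vs 90%. Uninjected as 0 of 3: 0.54 + 0.30·x vs 0.60·0.90 = 54%.
- Half uninjected. Recipients only: (0.80·0.90 + 0.15·x)/0.95 vs 90%. Uninjected as 0 of 3: 0.72 + 0.15·x vs 0.80·0.90 = 72%.

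| x | Recipients only, all | 0 of 3, all | Recipients only, half | 0 of 3, half |
|---|---|---|---|---|
| 100% | 93.3% vs 90% | 84% vs 54% | 91.6% vs 90% | 87% vs 72% |
| 90% | 90.0% vs 90% | 81% vs 54% | 90.0% vs 90% | 85.5% vs 72% |
| 80% | 86.7% vs 90% | 78% vs 54% | 88.4% vs 90% | 84.0% vs 72% |
| 70% | 83.3% vs 90% | 75% vs 54% | 86.8% vs 90% | 82.5% vs 72% |

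The recipients-only result favours placebo whenever x is below 90%.

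**4. Selection alone.** A simulation with 1,000,000 subjects per arm let treatment change the chance of injection (90% vs 60%) but not withdrawal afterwards (80% mild in both arms). Severity at Day 8 and later severity were bivariate normal with an assumed correlation.

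| Correlation | Recipients only | 0 of 3 |
|---|---|---|
| 0.3 | 81.9% vs 85.6% | 73.7% vs 51.3% |
| 0.5 | 83.5% vs 89.6% | 75.2% vs 53.8% |
| 0.7 | 85.4% vs 94.1% | 76.9% vs 56.4% |

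Among recipients, naltrexone looks about 4 to 9 points worse although treatment has no effect on later withdrawal. With 0 of 3 it leads by about 20 to 22 points.

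**The case against.** The strongest reply is that this is a scoring rule, which a statistical analysis plan commonly supplies, and that 0 of 3 could be adopted there without touching the analysis set. That is partly right, since a later document could add the rule. But the protocol has already fixed a tested endpoint and an analysis set that do not fit together, so the point is more than a missing detail.

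Several stronger readings are tempting and are not supported:
- **The protocol prescribes a recipients-only analysis.** It does not. Section 13.4 points to all dosed subjects. The reduction to recipients is what tends to follow from the endpoint's wording and from who is asked to attend.
- **Uninjected subjects cannot have COWS on Days 9-11.** Table 4 does not exclude them, and the days can be read as fixed study days. What stands is that no text asks these subjects to attend, and that any score they give is not post-VIVITROL.
- **Scores after buprenorphine restart will enter the endpoint and favour placebo.** The endpoint's own label already excludes them. Under Section 7.3 the early termination visit should be close to the withdrawal date, so it can precede Day 9, as can a stabilization stay after early discontinuation. Mainly Day 8/8a failures could give scores in the window. No size is claimed for this.
- **Section 8.4 and Table 4 footnote l flatly conflict.** Section 8.4 drops the assessments for subjects kept on the unit for stabilization on buprenorphine, while footnote l extends them to extra residential days. Footnote l refers to Section 8.4 for timing details, so Section 8.4 plausibly governs. This is a minor clarification.

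It is also fair to say that post-injection tolerability among recipients is a legitimate question, and that 0 of 3 credits reaching injection by construction.

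**Conclusion.** The point holds in this form: as written, the Days 9-11 comparison tends to rest on injected subjects, who are selected after randomization on COWS, and so is not a comparison of the randomized groups. At the planning rates the loss is at most about 4.6 vs 18.4 of 46 per arm, and 2.3 vs 9.2 if half of the failures were injected.

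That the direction can change is shown only under assumed mild-day rates and correlations. If the additional naltrexone recipients do as well as or better than the others, recipients only gives no difference or a small one in naltrexone's favour, and the harm is that the benefit on reaching injection is hidden. A reader might infer that the trial's main conclusion is at risk. It is not: the primary endpoint, its power and the key secondary endpoint are untouched by this point.

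**What to change.** In Section 13.4.3, state that for the between-group test in the safety population, dosed subjects who did not receive VIVITROL count as 0 of 3 mild days, in line with the primary endpoint's treatment of non-receipt as failure. Report recipients only as a descriptive summary. If the recipients-only question is the one intended, label it descriptive and do not present it as a randomized comparison.

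As a minor addition, reconcile Section 8.4 with Table 4 footnote l on whether COWS is recorded in Day 8/8a failures who stay on the unit, and say that scores taken after buprenorphine restart are not Days 9-11 data for this endpoint.

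The cost is wording and programming, with no new visits or subjects. The downside is overlap with the primary endpoint: with 90% mild days in all recipients, 81% vs 54% is simply 0.9 times 90% vs 60%. The descriptive summary is kept for that reason.
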